6.9.3 Sensitivity Analysis

In the presence of a high drop-out rate, performance of sensitivity analysis is crucial. The purpose of sensitivity analysis is to see whether different methods of handling missing data provide consistent and similar results for the primary efficacy analysis. To this end, the three sensitivity analyses will be performed:

1. Multiple imputation under MAR using available data on the primary endpoint
2. Placebo- based imputation under MNAR
3. Per Protocol Analysis

6.9.3.1 *Multiple imputation under Missing at Random (MAR)*

The multiple imputation (MI) method assumes that the missing data are missing at random (MAR), that is, the probability that an observation is missing may depend on the observed values but not the missing values. For example, if a subject's Diary values are available on Day 1 and Day 2 but missing on Day 3, then the missing value on Day 3 is related to the non-missing value on Day 1 and Day 2.

MI is implemented using the following three steps.

- 1) SAS PROC MI is applied with input dataset containing some missing values for all days during the titration and maintenance period to create 100 datasets. The data sets will include separate columns for the frequency of incidences during each day starting from baseline. The Markov Chain Monte Carlo (MCMC) method will be used to complete the missingness pattern to a monotone pattern separately by treatment arm. The monotone patterns will be achieved by applying sequential imputation based on Bayesian regression with the treatment arm included as a covariate. All copies contain identical values of the non-missing data items, but different values imputed for missing values.
- 2) For each of these MI data sets, the percent change will be computed as in the observed data set and the primary analysis based on the Wilcoxon rank-sum test will be conducted and asymptotic 95% confidence intervals will be constructed.
- 3) To produce a single confidence interval for each dose placebo comparison (e.g., Dose 1 versus placebo), PROC MIANALYZE will be used and Rubin's combination rules will be applied to the treatment effect estimates and associated asymptotic standard errors from the MI data sets.

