7 STATISTICAL ANALYSIS

7.1 *Analysis Populations*

The population of “all enrolled subjects” consists of all those screened subjects who meet the requirements for study participation and are entered in the Baseline period (i.e., distributed IA diary) of the study. The population of “all randomized subjects” consists of all those enrolled subjects who complete the Baseline Period, meet the inclusion/exclusion criteria and are randomized.

7.1.1 *Safety Population*

The safety population will include all randomized subjects who received at least 1 dose of study drug and have at least one post-randomization safety measurements.

7.1.2 *Intent-to-treat (ITT) Population*

The intent-to-treat population will include all subjects who received at least 1 dose of study drug and have a baseline and at least 1 valid post-randomization assessment of frequency of IA behaviors based on IA diary entry. Subjects will be analyzed according to the treatment to which they were randomized.

7.1.3 *Per Protocol (PP) Population*

The per protocol population will include all of the subjects in the ITT population who completed the treatment period (Completed Maintenance Visit 6) with 70% diary completion compliance and who did not have major protocol deviations. Diary compliance is calculated as

$$\text{diary compliance} = \frac{\text{number of days diary completed within the treatment period}}{\text{Number of treatment days}} \times 100\%$$

Detailed specification of the PP population will be provided prior to the database lock for the final analysis.

7.2 *Disposition of Subjects*

Subject disposition and reasons for screening failure will be summarized for screen-failed subjects (Table 14.1.1).

Subject randomization schedule will be listed. Subjects whose randomization codes are unblinded during the conduct of the study will be listed along with the reason for un-blinding (Listing 16.1.7).

The following summaries and listings will be based on all randomized subjects.

Subjects (n and %) who completed and discontinued from the study will be tabulated by the treatment group for (1) Randomized, (2) ITT, (3) Safety, and (4) PP populations (Table 14.1.2a – Table 14.1.2d). The primary reasons for study discontinuation will be included in the tabulation. The primary reasons may include any of the following:

- Subject withdrew consent
- Lost to follow-up
- Administrative reason
- Adverse event
- Investigator decision
- Failure to follow required study procedures
- Other

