where trtp is treatment group, bwk, twk1, twk2, twk3, twk4, and twk5 are variables of weekly IA scores during the baseline, and treatment (titration + maintenance) periods. These are derived as $(SUM/DAY)*7$, where SUM is the total of the IA scores reported on the IA diary in that analysis

week, and DAY is the number of days with non-missing IA score in the IA diary in that analysis week. Analysis week is defined as: 1st week is the 1st 7 days after visit 3 (exclusive) during titration, 2nd week is the rest of the days up to Visit 5 (inclusive) in titration period, 3rd week is the 1st 7 days after Visit 5 (exclusive), 4th week is the following 7 days after 3rd week, the 5th week is the rest of the days in maintenance period up to Visit 6 (inclusive). Adqs is the input data set with missing values, and adqs_imp is the complete imputed data set after 100 imputations. For the weekly IA score calculation, if the week has <3 daily diaries, the weekly IA score for this week will be set to missing and imputed using the above procedure.

From the above multiply-imputed IA data, the Hodges-Lehmann confidence interval will be calculated for each imputed data set. The point estimate for the between group difference and the associated standard error (SEM) will be derived from the confidence interval. These point estimates and the SEMs will be summarized by the SAS MIANALYZE procedure. A sample SAS code is as follows.

```
PROC MIANALYZE DATA=PARMEST ;
  MODELEFFECTS estim ;
  STDERR sem ;
  ODS OUTPUT PARAMETERESTIMATES=parmest2(KEEP= paramcd label estimate
                                             stderr lclmean uclmean probt) ;
  RUN ;
```

where estim and sem are the point estimate and SEM from each imputed set, estimate, stderr, lclmen, uclmean, and probt are the final summarized point estimate, standard error, lower and upper confidence limits, and the p-value for the between group comparison (Table 14.2.1.2.1).

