7.7.2.2 Multiple Imputation Assuming Missing Not at Random

This sensitivity analysis assumes that the diary data are missing not at random (MNAR), that is, the probability that an observation is missing may depend on its underlying unobserved value.

This approach may be considered “worst-case” sensitivity analyses as it assumes that after discontinuation subjects from the dosing arms would adopt the outcome model estimated from the placebo arm. To generate missing values from this “placebo-based” imputation model, PROC MI with the MNAR statement will be used (Table 14.2.1.2.2). A sample SAS code is as follows.

```
PROC MI DATA=adqs NIMPUTE=100 SEED=123456789 MINIMUM=0 OUT=adqs_imp ;
  CLASS trtp ;
  VAR age sex bwk twk1 twk2 twk3 twk4 twk5;
  FCS reg ;
  MNAR MODEL(bwk twk1 twk2 twk3 twk4 twk5 / MODELOBS=(trtp='Placebo')) ;
  RUN ;
```

where multivariate imputation is carried out by the fully conditional specification (fcs) method.

7.7.3 *Analysis of PCH Based on Data from Maintenance Period*

For this sensitivity analysis, the primary analysis will be repeated using data restricted to the maintenance period only (Table 14.2.1.2.3).

7.7.4 *Supplementary Analysis*

A supplementary analysis will be performed based on the Per Protocol population and will be presented in Table 14.2.1.2.4.

7.7.5 *Analysis Based on Adjustment of Covariates*

An exploratory analysis of the primary efficacy endpoint will be performed using a randomization-based approach (Dmitrienko and Koch 2017). Separate models will be produced for the following key prognostic baseline characteristics (age [categorical and continuous] and gender [categorical]) will be used in this analysis. In addition, pooled site and baseline IA adjusted to 7 days will be used as covariates (Table 14.2.1.4).

7.7.6 *Examination of Subgroups*

The primary and key secondary efficacy (Caregiver CGI-I and Investigator CGI-I) variables will be summarized by subgroup to explore the heterogeneity of the treatment effect across subgroups. This analysis will be done for the following subgroups: gender (male, female), age (6-9 and 10-12), and race (White, Black/African American, Other) (Table 14.2.1.5a - Table 14.2.1.5c).

7.7.7 *Secondary Efficacy Analyses*

All secondary analyses are based on the ITT population to compare the █ mg dose with the Placebo. The secondary analysis variables are:

1. Actual Caregiver CGI-I score at Visits 4, 5, and 6 (Table 14.2.2 and Listing 16.2.2.2)

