| 14.1.11 | Exposure to Study Medication and Compliance | ITT Population |
| 14.1.12.1 | Prior Medications by ATC Code and Preferred Term | Safety Population |
| 14.1.12.2 | Concomitant Medications by ATC Code and Preferred Term | Safety Population |
| 14.2.1.1 | Analyses of PCH in the Frequency of IA Behaviors During the Treatment Period - Primary Analysis | ITT Population |
| 14.2.1.2.1 | Analyses of PCH in the Frequency of IA Behaviors During the Treatment Period - Sensitivity Analysis, Multiple Imputation with MAR Assumption | ITT Population |
| 14.2.1.2.2 | Analyses of PCH in the Frequency of IA Behaviors During the Treatment Period - Sensitivity Analysis, Multiple Imputation with MNAR Assumption | ITT Population |
| 14.2.1.2.3 | Analyses of PCH in the Frequency of IA Behaviors During the Maintenance Period - Sensitivity Analysis | ITT Population |
| 14.2.1.2.4 | Analyses of PCH in the Frequency of IA Behaviors During the Treatment Period - Supplementary Analysis | PP Population |
| 14.2.1.3 | Descriptive Statistics for Frequency of IA Behaviors Per 7 Days and Change from Baseline by Study Period | ITT Population |
| 14.2.1.4 | Percent Change from Baseline to Treatment Period in Frequency of IA Behaviors: Adjustment for Covariates using Randomization-Based Approach of Dmitrienko and Koch | ITT Population |
| 14.2.1.5a | Analyses of PCH in the Frequency of IA Behaviors During the Treatment Period by Gender - Primary Analysis | ITT Population |
| 14.2.1.5b | Analyses of PCH in the Frequency of IA Behaviors During the Treatment Period by Age - Primary Analysis | ITT Population |

| | | |
|-----------|--|----------------|
| 14.2.1.5c | Analyses of PCH in the Frequency of IA Behaviors During the Treatment Period by Race - Primary Analysis | ITT Population |
| 14.2.2 | Investigator Clinical Global Impression – Improvement (CGI-I) Score by Visit | ITT Population |
| 14.2.3 | Caregiver Clinical Global Impression – Improvement (CGI-I) Score by Visit | ITT Population |
| 14.2.4 | Investigator Clinical Global Impression – Severity (CGI-S) Score and Change from Baseline by Visit | ITT Population |
| 14.2.5.1 | Child Health Questionnaire Parent Form 28 (CHQ-PF28) - Item Scores and Change from Baseline to Visit 6 | ITT Population |
| 14.2.5.2 | Child Health Questionnaire Parent Form 28 (CHQ-PF28)-Component Scores and Change from Baseline to Visit 6 | ITT Population |

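### The placebo-based sensitivity analysis leaves out dosed children with no post-randomisation diary, and its code applies the placebo model to more weeks than its text describes

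*SAP*

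**What the plan says.** **Assumption.** SAP 7.7.2.2 states that "after discontinuation subjects from the dosing arms would adopt the outcome model estimated from the placebo arm". It says the approach may be considered a worst case. Protocol 6.9.3.2 states the same assumption and uses the same label.

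**Code.** The sample program in SAP 7.7.2.2 contains "MNAR MODEL(bwk twk1 twk2 twk3 twk4 twk5 / MODELOBS=(trtp='Placebo". No variable marks discontinuation.

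**Population.** SAP Appendix 2 lists Table 14.2.1.2.2 as "Multiple Imputation with MNAR Assumption | ITT Population". SAP 7.1.2 admits to ITT children who took a dose and "have a baseline and at least 1 valid post-randomization assessment of frequency of IA behaviors based on IA diary entry". Protocol 6.3 sets the same condition.

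**When a week is missing.** Step 1 of SAP 7.7.2.1 sets a weekly score to missing only when no day of that week has a score. The paragraph after the sample code says that "if the week has <3 daily diaries, the weekly IA score for this week will be set to missing and imputed using the above procedure". Weeks that are kept are scaled up from the days available.

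**Dates.** SAP 6.4 distinguishes days after discontinuation from other missed diary days, and it uses a last-dose date recorded on the End of Study form.

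**The concern.** A placebo-based analysis is there to show whether the result survives if children lost from the active arms did no better than placebo. Two features blur that.

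1. **Children.** The baseline period runs to Day 1 (SAP 4) and treatment-period diaries start on Day 2 (SAP 5.1). A child who takes a first dose and is lost before any later entry drops out of ITT, and so out of both the primary analysis and this one. Such children could be imputed, because randomisation requires at least 12 of 15 baseline diaries. The boundary is also uneven. Under the fewer-than-3 rule, a child with one or two diaries in week 1 who then leaves has all five weeks imputed, while a child with none is excluded.
2. **Weeks.** The text limits the placebo model to time after discontinuation. The code also covers a missing week in a child still taking drug. It does not reach the days after stopping in a week that already has three or more diaries, because that week is kept and scaled up.

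At stake is how a reader may describe a result that passes this analysis, above all if it is presented as a worst case.

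**Working it through.** **Base figures (SAP 3.5).** Difference 15, SD 34.83, 90% power, two-sided 0.05, Wilcoxon rank-sum, 122 per arm, 20% dropout, 153 randomised per arm.

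Reproduction with the Noether formula, n = (1.960 + 1.282)² / [6(p − 0.5)²], where p = Φ(15 / (34.83 × √2)) = 0.6196:
- n = 122.35, against the stated 122
- 122 / 0.8 = 152.5, which rounds up to the stated 153

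**Omitted children.** Suppose k of 153 children in an active arm have no post-randomisation diary and would follow placebo. The effect over all 153 is 15 × (153 − k) / 153. This is exact for a mean and approximate for the Hodges-Lehmann estimate. Power is Φ(√(6n) × (p − 0.5) − 1.960), with n = 153 per arm for all dosed children and n = 153 − k per arm for ITT only.

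| k | Effect | Power, all dosed | Power, ITT only |
|---|---|---|---|
| 0 | 15.0 | 95.2% | 95.2% |
| 2 | 14.8 | 94.7% | 95.0% |
| 5 | 14.5 | 93.9% | 94.6% |
| 15 | 13.5 | 90.6% | 93.1% |
| 31 | 12.0 | 82.8% | 89.9% |

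The documents do not give k. The last row treats the whole planned dropout (153 − 122 = 31) as having no diary. It is an upper bound, since one entry is enough for ITT.

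**On-study missing weeks.** Take the fewer-than-3 rule, a 7-day week and independent daily completion at rate c. The chance that a week is set to missing is P(Binomial(7, c) ≤ 2):
- c = 80%: 0.5%
- c = 70%: 2.9%
- c = 50%: 22.7%

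If such a week lost its whole effect, and weeks count equally, the estimate would fall by that fraction of 15:
- c = 80%: 0.0047 × 15 = 0.07 points
- c = 70%: 0.0288 × 15 = 0.43 points

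These are ceilings, because the imputation also conditions on the child's own observed weeks.

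Weeks 2 and 5 take whatever days remain. With visits at the short end of their windows they last 12 − 7 = 5 days and 18 − 14 = 4 days. At 80% completion the chance of fewer than 3 diaries is then 5.8% and 18.1%; at 70% it is 16.3% and 34.8%. Those are extremes of the visit windows, not typical values.

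**Direction.** An illustrative simulation used log-scale weekly scores, 110 per arm, 20 to 30% active-arm dropout and a true difference of about −17. Hodges-Lehmann differences were:

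| Missing on-study weeks | MAR | Text rule | Code rule | Text rule plus no-diary children |
|---|---|---|---|---|
| 5% | −16.22 | −15.42 | −15.37 | −14.99 |
| 10% | −16.36 | −15.29 | −15.09 | −14.54 |
| 15% | −17.85 | −16.95 | −16.65 | −16.50 |

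The code rule gives a slightly smaller effect than the text rule, by 0.05 to 0.30 points. Adding no-diary children to the text rule (assumed 3 to 6% active, 1 to 2% placebo) shrinks it by 0.43 to 0.75. Those rates are assumptions, and PROC MI itself was not run.

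**The case against.** The strongest defence is that a sensitivity analysis should vary one thing. Protocol 6.9.3 aims to see whether different missing-data methods agree with the primary analysis, and holding the population at ITT does that. The code is labelled a sample, and the SAP says only that the approach may be considered a worst case. This stands as a reason to keep the ITT table. It is no reason against a second set, because no other planned efficacy analysis covers children without a post-randomisation diary.

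A reader might infer more than the documents support:
- **That every diary gap is treated as discontinuation.** It is not. Weeks with three or more diaries are scaled up and never imputed. With 7-day weeks, about 98% of missed on-study days fall in such weeks at 80% completion, and 93% at 70%.
- **That the stated assumption goes untested.** For an ITT child who stops, later missing weeks are drawn from the placebo model as described. Where code and text differ on on-study weeks, the code is usually a little harder on the drug.
- **That the SAP dropped a protocol safeguard from this analysis.** The step reading "The Markov Chain Monte Carlo (MCMC) method will be used to complete the missingness pattern to a monotone pattern separately by treatment arm" belongs to the protocol's MAR section. Its MNAR section has no such step.
- **That imputing baseline distorts the result.** Listing bwk has no effect within ITT, where a baseline is required.
- **That the omitted children are the worst cases.** Their outcomes are unobserved.

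**Conclusion.** The point holds in a limited form. The placebo-based analysis excludes dosed children who have a baseline but no post-randomisation diary, and this can favour the drug. With 5 of 153 omitted per active arm, 15 points becomes about 14.5. The figure rests on those children following placebo and on a count that the documents do not report.

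The mismatch between text and code is real but small, at most 0.07 to 0.43 points with 7-day weeks and 70 to 80% daily completion. It usually pulls towards no effect. Completion well below that range, or many visits at the short end of their windows, would enlarge it.

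The two missing-week rules in SAP 7.7.2.1 leave the set of imputed weeks undefined. None of this alters the primary analysis or invalidates the sensitivity analysis. It limits what a pass can be said to show, and it is cheap to put right.

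**What to change.** 1. Keep Tables 14.2.1.2.1 and 14.2.1.2.2 on ITT for comparability. Add the same MAR and MNAR analyses on all randomised, dosed children with a baseline diary, and report the number without a post-randomisation diary by arm.
2. In the MNAR analysis, use the collected last-dose or discontinuation date as a flag. First impute missing weeks before discontinuation within arm under MAR. Then impute post-discontinuation weeks, and all weeks for no-diary children, from the placebo model.
3. Choose one missing-week rule in SAP 7.7.2.1 and state that it applies to both analyses.
4. Do not describe the ITT-only result as worst-case.

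The cost is SAP wording before unblinding, one extra PROC MI step, supplementary tables, and possibly a slightly less favourable sensitivity estimate. No new data are needed.

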4 DEFINITIONS AND DERIVED DATASETS

Table 1. Terminology and Definition

| Terminology | Definition |
|-------------------------|---|
| Study Medication | SPN-810 or the matching placebo. |
| Study Day | The first dose date (Day 1) is defined as the date on which a subject took the first dose of double-blind study medication (SM), Other study days are defined relative to the Study Day 1. For visits prior to the first dose of the SM, Study Day is calculated as Visit Date – Day 1. For visits after the first dose, Study Day is calculated as Visit Date – Day 1 +1. |
| Enrolled | Subject has provided signed informed consent. |
| Randomized | Subject is assigned with the kit number for the SM. |
| Completer for the Study | Subject who completes the maintenance period (Visit 6). |
| Baseline | Unless specified otherwise, baseline is defined as the non-missing value collected most recent to and before the time of the very first dose of the SM. |
| Baseline Period | For subject daily IA diaries, on and prior to Visit 3 (inclusive, ≤Day 1). |
| Prior Medication | Medication collected on the Prior/Concomitant Medication CRF, with the start date prior to Study Day 1. |
| Concomitant Medication | Medication collected on the Prior/Concomitant Medication CRF, with end date on/after Study Day 1. |
| Titration Period | For subject daily IA diaries from Visit 3 through Visit 5 (v3< to ≤ V5) |
| Maintenance Period | For subject daily IA diaries from Visit 5 through Visit 6 (V5< to ≤ V6) |
| Treatment Period | Titration and Maintenance Periods combined |
| Derived Dataset | Derived dataset (analysis dataset) is any permanently stored collection of data containing raw and/or derived variables created to support the production of statistical summary tables. Derived variables will be created from the “raw” data. Analysis datasets to be created will include ADEFF (efficacy analysis dataset), ADSL (subject-level analysis dataset), ADAE (Adverse event analysis dataset) and other as appropriate. In deriving ADEFF, the source data include both the episodic diary and evening diary data files. Specifications for derived datasets will be developed which will include the names and definitions of derived variables in the derived SAS datasets. |

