6.4 Handling of Dropouts, Missing Data, and Data Discrepancies

For the primary analysis of the primary efficacy endpoint, the frequency of IA behaviors during the treatment (titration + maintenance) period will be calculated over the number of days with non-missing IA diary data in the treatment period. No explicit imputation of missing data will be used, but this approach is implicitly equivalent to using the frequency of IA behaviors during the days with non-missing IA diary data to impute the frequency for days after study discontinuation or days with missing IA diary data. In addition to this implicit imputation, multiple imputations under the assumption of missing at random (MAR) and missing not at random (MNAR) will be used for handling missing data for sensitivity analysis. Details of imputation methods are specified in Section [7.7.2](#).

For analysis of frequency of IA behaviors during the treatment period (titration or maintenance), the following methods will be followed.

- 1) If subjects discontinued the study during the maintenance period, their maintenance period will be counted from Visit 5 (exclusive) through the date of last dose as documented on the End of Study eCRF page (inclusive). If the date of last dose is not collected, it will be imputed by the subjects' last visit for the study.
- 2) If subjects have ≥ 7 daily diaries in the maintenance period, their maintenance IA frequencies will be based on maintenance daily diaries.
- 3) If subjects have <7 daily diaries in the maintenance period, their maintenance IA frequencies will be calculated pooling the titration period diaries with the maintenance period diaries.
- 4) If subjects do not have any maintenance diaries, their maintenance IA frequencies will be entirely derived from the titration period diaries.

Missing data for secondary efficacy endpoints will be handled by using the Mixed Model for Repeated Measures method, which is implemented via SAS® PROC MIXED procedure. MMRM assumes data are “Missing At Random (MAR)”. That is, the probability that an observation is missing may depend on the observed values but not the missing values in the previously scheduled visits.

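### The maintenance-only sensitivity analysis (SAP 7.7.3) takes in titration diaries, through SAP 6.4, for every subject with fewer than 7 maintenance diaries

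*SAP*

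**What the plan says.** SAP 7.7.3 is one sentence: for this sensitivity analysis, "the primary analysis will be repeated using data restricted to the maintenance period only". The output is Table 14.2.1.2.3, which SAP Appendix 2 describes as covering the maintenance period in the ITT population. Section 7.7.3 states no exception and does not refer to 6.4.

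SAP 6.4 gives the derivation rules, introduced by "For analysis of frequency of IA behaviors during the treatment period (titration or maintenance), the following methods will be followed". They are:

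- Rule 1 sets the end of the maintenance period for subjects who discontinue during it.
- Rule 2, for at least 7 maintenance diaries: "their maintenance IA frequencies will be based on maintenance daily diaries".
- Rule 3: "If subjects have <7 daily diaries in the maintenance period", then "their maintenance IA frequencies will be calculated pooling the titration period diaries with the maintenance period diaries".
- Rule 4, for no maintenance diaries: "their maintenance IA frequencies will be entirely derived from the titration period diaries".

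SAP section 4 defines titration as the days after Visit 3 up to Visit 5, and maintenance as the days after Visit 5 up to Visit 6. Protocol 3.2 describes titration as the escalation phase, and protocol 3.2.2.3 has the designated dose held for the three weeks of maintenance. The primary endpoint (SAP 5.1) uses both periods together.

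**The concern.** The primary endpoint averages over two weeks of escalation and three weeks of maintenance. A reader who wants to know whether the result holds once escalation is left out will turn to Table 14.2.1.2.3. If rules 3 and 4 feed that table, subjects with few or no maintenance diaries enter it with mostly or wholly titration data under a maintenance label.

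The ITT definition (SAP 7.1.2) needs only a dose, a baseline and one valid post-randomization diary assessment, so subjects who leave during titration are included. If early departure differs by arm, so does the mix of titration and maintenance data behind each arm's result.

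**Working it through.** **1. The two sections side by side**

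| Maintenance diaries | SAP 6.4 uses | Fits SAP 7.7.3? |
|---|---|---|
| 7 or more | maintenance only | yes |
| 1 to 6 | titration and maintenance pooled | no |
| 0 | titration only | no |

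**2. Titration share of the value**

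Let t be the number of titration diaries and k the number of maintenance diaries. Under rules 3 and 4 the titration share is t/(t + k). With t = 14 (nominal titration length, every diary complete):

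| k | Share |
|---|---|
| 0 | 14/14 = 100% |
| 1 | 14/15 = 93% |
| 3 | 14/17 = 82% |
| 6 | 14/20 = 70% |
| 7 | 0% (rule 2 applies) |

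The Visit 5 window in SAP Table 1 allows 12 to 16 days, which gives 12/18 = 67% to 16/22 = 73% at k = 6. One further diary, from 6 to 7, takes the share from about 70% to zero.

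**3. Comparison with the primary value**

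SAP 5.1 defines the frequency as (SUM/DAY) × 7 over the treatment period. Write S and D for the behaviors and diary days in titration (T) and maintenance (M).

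- Primary: (S_T + S_M)/(D_T + D_M) × 7.
- Rule 3: the same expression.
- Rule 4: D_M = 0, so both reduce to S_T/D_T × 7.

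Apart from any effect of rule 1's end date, an affected subject's maintenance percent change is therefore the primary percent change. The analysis tests nothing new in that subject.

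**4. Who is affected**

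The documents give no count. A completer with 6 diaries over a nominal 21 days would have 6/21 = 29% completion, yet randomization required at least 80% in baseline (protocol 4.1.1). This suggests, but does not show, that most affected subjects leave in titration or early maintenance.

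**5. Illustration of scale**

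The plan states no figure for this analysis. The nearest is the sample size in SAP 3.5, which the Noether formula for the Wilcoxon test reproduces: n = (1.960 + 1.282)²/[6(p − 0.5)²], with p = Φ(δ/(SD√2)).

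- δ = 15, SD = 27.3: 76.6 per arm (stated 77).
- δ = 15, SD = 34.83: 122.4 per arm (stated 122).

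Now assume that 15 is the effect in maintenance, a share f of subjects is affected, their titration weight is w (0.70 to 1.00), and the titration effect is a fraction r of the maintenance effect. The values of f and r are not in the documents. The diluted effect is 15 × [1 − f·w·(1 − r)].

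| f | r | Effect | Power at 77 or 122 per arm |
|---|---|---|---|
| any | 1 | 15.0 | 90% |
| 5% | 0.5 | 14.6 to 14.7 | 88% to 89% |
| 20% | 0.5 | 13.5 to 14.0 | 83% to 86% |
| 20% | 0 | 12.0 to 12.9 | 74% to 80% |

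For example, 15 × (1 − 0.20 × 1.00 × 0.5) = 13.5. Protocol 6.10 assumes 11.51 in place of 15; the proportional reduction would be the same. The formula assumes equal f in all arms and r of at most 1. With unequal dropout the direction could differ.

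**The case against.** The best reply is that 6.4 is the operational definition and 7.7.3 merely names the variable. Rules 2 to 4 expressly cover the maintenance frequency, the SAP's summary of changes records the 6.4 text as a deliberate expansion for incomplete data, and a programmer could apply the specific rule. The rules also keep every ITT subject in the analysis, and any alternative needs its own missing-data assumption. All of that is fair. But on this reading the table still presents titration-dominated values as maintenance results, so the label is wrong and the check is empty for the subjects concerned.

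It is also fair that filling weeks by imputation does not remove titration entirely, because the model in 7.7.2.1 uses titration weeks as predictors. There they inform a modelled maintenance value. Under rules 3 and 4 they stand in for it.

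Several stronger readings are tempting, and the documents do not support them:

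- **That every borrowed day is below the target dose.** The dose steps in protocol Table 2 are redacted, and protocol 3.2 says only that dose rises about every 3 days until target. Late titration days may already be at target.
- **That this is the only planned look free of titration.** Protocol 6.12 plans visit-level percent change, which SAP section 1 leaves to a separate analysis, and SAP 7.7.1 lists weekly frequencies. What holds is narrower: 7.7.3 is the SAP's only dose-versus-placebo test of the diary endpoint meant to exclude titration.
- **That one subject in five is affected.** The 20% in SAP 3.5 is all dropout before completion. It includes subjects who leave after 7 or more maintenance diaries, and it is applied as loss between randomization and the ITT set. It serves only as an upper illustration.
- **That 7.7.3 promises the effect at the maintained dose.** It does not use those words.

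**Conclusion.** The conflict between SAP 7.7.3 and SAP 6.4 is real and stands in the text. For subjects with fewer than 7 maintenance diaries, the analysis described as maintenance-only is mostly or wholly escalation-phase data: about 70% at 6 diaries and 100% at none, if 14 titration diaries are complete. It essentially repeats their primary-endpoint value.

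The number of such subjects, and the size and direction of any bias in the treatment comparison, cannot be computed from the documents. The illustration runs from no change to a drop from 15 to 12.0, depending wholly on assumed inputs. The primary analysis, its type I error control and the interim rules are unaffected. The point concerns one sensitivity analysis, but its stated purpose depends on it, and it should be settled before database lock.

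**What to change.** For Table 14.2.1.2.3:

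- Do not apply rules 3 and 4 of SAP 6.4. Use maintenance diaries only.
- Fill missing maintenance weeks (twk3 to twk5) from the missing-at-random imputation in SAP 7.7.2.1, not the placebo-based set in 7.7.2.2. Keep its rule that a week with fewer than 3 diaries is set to missing, and combine the Hodges-Lehmann estimates by Rubin's rules as already specified there.
- State how the three weekly values form the maintenance frequency.
- Report, per arm, the number of subjects with fewer than 7 and with no maintenance diaries.

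If the rules 3 and 4 version is also kept, label it as including titration data and remove the maintenance-only wording from its description.

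The cost is a short SAP edit and reuse of imputed data that the plan already produces. The interval may be slightly wider, and the result relies on missing at random.
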